7.3 Evaluation of safety

7.3.1 Adverse events

All adverse events will be recorded; the investigator will assess whether those events are drug-related (reasonable possibility, no reasonable possibility) and this assessment will be recorded in the database for all adverse events. A change in grading will be collected by giving an outcome date to the initial AE. A new adverse event needs to be reported to reflect the change in severity.

The collection period will start from patient enrollment.

All adverse events will be followed until resolution while the patient remains on study treatment. When the patient discontinues study treatment, suspected adverse reactions (AEs for which there is a reasonable possibility that the drug caused the AE) that started while on study treatment should be followed for 30 days from the date of the last dose of study drug or until considered chronic/ stable (as judged by the Investigator), whichever comes first.

New SAEs and serious suspected adverse reactions that occur during the 30-day period should be reported and followed until resolved or considered stable / chronic (as judged by the Investigator).

7.3.2 General evaluation of adverse events

This study will use the International Common Terminology Criteria for Adverse Events (CTCAE), version 5.0, for adverse event reporting. A copy of the CTCAE can be accessed from the EORTC home page <https://www.eortc.be/services/doc/ctc/>.

Hematological and biochemistry adverse events will be assessed on the basis of at least monthly blood counts, except weekly for the first cycle.

The highest CTCAE grading per cycle and per patient will be computed at the EORTC HQ for analysis.

Planned safety analysis and tabulations are described in the statistics section.

Serious adverse events are defined by the Good Clinical Practice Guideline.

Serious adverse events should be immediately reported according to the procedure detailed in this Protocol (see chapter 15 on Reporting Serious Adverse Events).

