5.2.1.1 Group A

Patients with MGMT promoter-unmethylated AA or GBM will receive TG02 orally twice weekly in combination with radiation therapy (RT).

TG02 and RT can start on the day of enrollment but no more than 7 days after enrollment. TG02 will be administered on days 1, 4, 8, 11, 15 and 18. Standard involved-field hypofractionated RT will be administered at 39.9 Gy in 15 fractions of 2.66 Gy for 3 weeks (days 1-21).

Seven days after completing combination therapy, patients will receive maintenance cycles of single agent TG02. TG02 will be administered on days 1, 4, 8, 11, 15, 18, 22 and 25 of each 28-day maintenance cycle.

DOSE ESCALATION

The dose escalation scheme for TG02 is provided below. Three patients will be enrolled at 100 mg.

- If no patient in this cohort of 3 patients experiences a DLT, the dose will be escalated and 3 patients enrolled at 150 mg.
- If 1 patient in the cohort of 3 patients experiences a DLT, 3 additional patients will be enrolled at 100 mg. If none of the additional 3 patients experiences a DLT, the dose will be escalated and 3 patients enrolled at 150 mg.
- If the DLT criteria are not met (i.e., no patients with DLT out of 3 patients or ≤ 1 DLT out of 6 patients) at 150 mg, then, 150 mg TG02 will be declared the MTD for expansion.
- If > 1 out of 3 patients or ≥ 2 out of 6 patients experiences a DLT at 150 mg, dose escalation will not proceed and 100 mg will be considered the maximum MTD.
- If > 1 out of 3 patients or ≥ 2 out of 6 patients experiences a DLT at 100 mg, the arm will be closed

Patients who have not experienced any DLTs at the end of their first cycle will continue at the same TG02 dose for the subsequent cycles, unless they experience a severe side effect needing a dose reduction or delay (see section 5.5 for specific instructions).

TG02 Citrate Capsules Dose Escalation Scheme

Dose Level (Cohort)	Dose (mg)	# Units/ Capsule Strength (mg)	
		50	150
0	100	2	0
1	150	0	1

The Dose-Limiting Toxicity (DLT) for group A will be defined as any of the following adverse events occurring during cycle 1 that are considered clinically significant and there is a reasonable possibility that the AE is related to the combination treatment by the clinical investigator:

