- Any non-hematological grade III–IV toxicity according to CTCAE, Version 5.0 with the exclusion of alopecia and asymptomatic or reversible laboratory abnormalities which can be rapidly controlled with appropriate measures. This acute toxicity must be declared as possibly related by the clinical investigator in order to be taken into account in the decision rule.
- An absolute neutrophil count $< 0.5 \times 10^9/L$ lasting for ≥ 7 days
- Febrile neutropenia defined as an absolute neutrophil count $< 0.5 \times 10^9/L$ and fever of at least $38.5^\circ C$
- Thrombocytopenia grade III with bleeding or any grade IV according to CTCAE, Version 5.0

- Nausea, vomiting or diarrhea grade III-IV not controlled after 48 h of maximal antiemetic or antidiarrheal treatment
- Any toxicity not qualifying for DLT but which does not allow intake of 75% of intended dose intensity of TG02 or of RT

EXPANSION

After dose escalation is completed, additional patients will be enrolled at MTD up to a total of 24 evaluable patients in Group A. Expansion at the predetermined MTD will be stopped if 2 or more of the first 6 patients, or 33% or more of the patients thereafter, experience a DLT. The expansion cohort will be fully enrolled at the next lower dose level. If there are again 2 DLT in the first 6 patients, expansion will be stopped in that arm.

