6.2 Study treatment phase

6.2.1 Cycle 1 for Group A

All cycles are 28 days. Cycle 1 is 21 days of RT and a 7-day break. Cycle 2 will begin after completion of combination TG02 and RT treatment, including the 7 day break.

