6.2.1.2 Every week (Days 8 and 15)

- Concomitant medications assessment
- Steroid dose. For corticosteroids, dose, frequency, dates of administration and route of administration must be recorded in the dedicated eCRF.
- Vital signs: blood pressure, pulse, temperature, weight
- Karnofsky Performance Status (KPS) (see Appendix E)
- Hematology: includes hemoglobin, hematocrit, total WBC count with differential (neutrophils and lymphocytes), and platelet count

- Biochemistry: sodium, potassium, chloride, BUN, creatinine, total protein, albumin, AST and/or ALT, total bilirubin, alkaline phosphatase, calcium, magnesium, LDH, glucose, creatinine kinase and phosphate
- Adverse events assessment (see section 7.3.1)
- TG02 compliance

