6.4 Summary tables

6.4.1 Summary table for Group A

All cycles are 28 days. Cycle 2 will begin 7 days after completion of combination treatment.

GROUP A	Registration		Enrollment	Cycle 1, Day 1 pre-dose	Cycle 1, Days 8, 15	Study Treatment ² Phase		End of treatment ²⁰	Follow Up
	Within 28 days of enrollment ²	Within 14 days of enrollment				Safety / Prescription ¹⁸	Efficacy ¹⁹		
Histological diagnosis of glioblastoma or AA	X								
Signed informed consent	X								
FFPE block or 25 unstained slides sent to [REDACTED]	X								
Medical history, including prior cancer	X								
Determination of MGMT promoter-methylation status			X						
Complete physical examination ³		X						X	
Concomitant medications assessment		X		X	X	X		X	
Steroid dose ⁴		X		X	X	X		X	
Vital signs ⁵		X		X	X	X		X	
Karnofsky Performance Status (KPS) ⁶		X		X	X	X		X	
Hematology ⁷		X		X	X	X		X	
Biochemistry ⁸		X		X	X	X		X	
Coagulation ⁹		X		X		X		X	
Adverse events evaluation ¹⁰				X	X	X		X	

GROUP A (continued)	Registration		Enrollment	Cycle 1, Day 1	Cycle 1, Days 8, 15	Study Treatment Phase		End of treatment ²⁰	Follow Up
	Within 28 days of enrollment ²	Within 14 days of enrollment				Within 7 days of enrollment	Safety / Prescription ¹⁸		
TG02 prescription (+prophylaxis) ¹¹				X		X			
TG02 compliance evaluation ¹¹					X	X		X	
Radiotherapy ¹²				X	X				
12-Lead ECG ¹³		X							
Brain Gd-MRI ¹⁴		X ²					X	X	X ¹⁴
Neurological examination (NANO) ¹⁵		X					X	X	
Quality of life assessment (modified EORTC QLQ C30/BN20) ¹⁶		X					X	X	X ²²
Geriatric evaluation ¹⁷		X							
Optional translational research ²¹		X				X		X	
Survival follow-up ²²									X

¹ Tissue must be sent to [REDACTED] for MGMT analysis as soon as the patient has signed the consent form. Results are needed before enrollment onto the study for Group A.

² Brain Gd-MRI must be completed within 14 days of first dose of TG02. If a 72-hour post-surgery MRI was done and falls within this time window, baseline MRI does not need to be repeated.

³ Complete physical examination will be done at registration and end of study visit. The examination should include any ongoing clinical symptoms. For female patients, menopausal status should be documented.

⁴ For corticosteroids, dose, frequency, dates of administration and route of administration must be recorded in the dedicated eCRF.

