⁵ Blood pressure, pulse, temperature, weight and height will be collected at registration. At all other times, blood pressure, pulse, temperature and weight will be collected.

⁶ See Appendix E.

⁷ Hemoglobin, hematocrit, total WBC count with differential (neutrophils and lymphocytes), and platelet count will be measured at registration, Cycle 1 Day 1 pre-dose, Cycle 1 Days 8 and 15, on Day 1 of subsequent cycles, and at the end of study visit. If the registration hematology panel is done within 72 h of pre-dose on Cycle 1 Day 1, it does not need to be repeated.

⁸ Sodium, potassium, chloride, BUN, creatinine, total protein, albumin, AST and/or ALT, total bilirubin, alkaline phosphatase, calcium, magnesium, LDH, glucose, creatinine kinase and phosphate will be measured at registration, Cycle 1 Day 1 pre-dose, Cycle 1 Days 8 and 15, on Day 1 of subsequent cycles, and at the end of study visit. If the registration chemistry panel is done within 72 h of pre-dose on Cycle 1 Day 1, it does not need to be repeated.

⁹ PT, PTT, and INR will be measured at registration, Cycle 1 Day 1 pre-dose and at the end of study visit. If the registration coagulation panel has been done within 72 hours of pre-dose on Cycle 1 Day 1, it does not need to be repeated.

¹⁰ Adverse events grading according to CTCAE 5.0

¹¹ TG02 and RT can start on the day of enrollment but no more than 7 days after enrollment. TG02 is given on Days 1, 4, 8, 11, 15 and 18 of the first cycle in combination with RT. Skipped doses of TG02 will be noted in the patient study drug diary. On days when both TG02 and RT are scheduled, TG02 will be taken approximately 1 hour before RT treatment. TG02 is given on Days 1, 4, 8, 11, 15, 18, 22 and 25 of maintenance cycles. See section 5.2.1.1.

¹² TG02 and RT can start on the day of enrollment but no more than 7 days after enrollment. Standard involved-field radiotherapy (40 Gy in 15 fractions of 2.66 Gy for 3 weeks). See Section 5.7.

¹³ ECG should be repeated if medically indicated.

¹⁴ Brain Gd-MRI will be done every 2 cycles (\pm 8 days) until 6 cycles, then every 3 cycles (\pm 8 days). If treatment is stopped before progression is observed, brain Gd-MRI should be done every 3 months (\pm 14 days). See Appendix J for detailed MRI sequences. Additional details can be found in the study specific imaging guideline.

¹⁵ NANO scale (see section 7.2.4).

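### Group A has no scheduled blood count between Day 15 and Cycle 2 Day 1, although section 7.3.2 says counts are weekly in cycle 1, so a silent late hematological DLT could go unseen

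*Combined protocol and SAP*

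**What the plan says.** - **General rule.** Section 7.3.2: "Hematological and biochemistry adverse events will be assessed on the basis of at least monthly blood counts, except weekly for the first cycle".
- **Length of Group A cycle 1.** Section 6.2.1 makes every cycle 28 days and puts the rest week inside the first: "Cycle 1 is 21 days of RT and a 7-day break".
- **Group A schedule.** The 6.4.1 table column reads "Cycle 1, Days 8, 15". Footnotes 7 and 8 give the post-registration times for hematology and biochemistry as "Cycle 1 Day 1 pre-dose, Cycle 1 Days 8 and 15, on Day 1 of subsequent cycles". Section 6.2.1.2 lists the same two days. None of the three contains Day 22.
- **Treatment.** Section 5.2.1.1 gives TG02 on Days 1, 4, 8, 11, 15 and 18, with radiotherapy over Days 1 to 21.
- **DLT definition.** Section 5.2.1.1 covers "any of the following adverse events occurring during cycle 1", provided the investigator considers the event clinically significant and reasonably possibly related to the combination. Two criteria can be met without symptoms: "Thrombocytopenia grade III with bleeding or any grade IV according to CTCAE, Version 5.0" (its grade IV limb), and a neutrophil count below 0.5 x 10^9/L "lasting for ≥ 7 days".
- **Escalation.** Section 8.1.1 allows the second dose level to open once all patients at the first have completed the 28-day cycle 1. Section 18.1 calls for a teleconference at the end of each dosing cohort.

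**The concern.** The general rule and the Group A schedule disagree, and they disagree inside the DLT window. After the Day 15 count a patient receives the Day 18 TG02 dose and the third week of radiotherapy, and no count is scheduled before the cycle ends. A hematological event without fever, bleeding or other symptoms can only be found by a blood count.

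The MTD and the recommended phase II dose are Group A's primary endpoints, and they are decided on cohorts of 3 to 6 patients, where one DLT can change the decision. A missed DLT never lowers the chosen dose. It can only help a dose level pass. The expansion stopping rule counts DLTs on the same blood-count schedule.

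**Working it through.** The plan states no figure to reproduce, so the check is a count of days.

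**Inputs.** Group A counts on Days 1, 8 and 15 (6.2.1.2; 6.4.1 footnotes 7 and 8). Cycle 2 Day 1 (C2D1) on Day 29 with a ±3-day window (6.2.4), so Day 26, 29 or 32. Last combination TG02 dose on Day 18 (5.2.1.1).

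**Rule.** An episode of d days starting on day s is unseen if no scheduled count falls in days s to s+d-1.

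**Formulas.**
- Gap after Day 15 = C2D1 - 15.
- Delay after the Day 18 dose = C2D1 - 18.
- Longest unsampled run = C2D1 - 16 days.
- Unseen start days for a 7-day episode = run - 6, or 0 if that is negative.
- With Day 22 added, the run splits into Days 16-21 (6 days) and Day 23 to the day before C2D1 (C2D1 - 23 days).

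| C2D1 | Gap | After Day 18 dose | Longest run | 7-day starts unseen now | With Day 22 | Weekly until C2D1 |
|---|---|---|---|---|---|---|
| Day 26 | 11 | 8 | 10 | 4 (Days 16-19) | 0 | 0 |
| Day 29 | 14 | 11 | 13 | 7 (Days 16-22) | 0 | 0 |
| Day 32 | 17 | 14 | 16 | 10 (Days 16-25) | 3 (Days 23-25) | 0 |

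Between the earlier cycle 1 counts the longest unsampled run is 6 days. On the nominal calendar the last run is 13 days, so a neutrophil episode of 7 to 13 days fits inside it, as does a grade IV platelet fall of up to 13 days.

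**Short platelet falls.** Assume a 3-day fall starting on any of Days 16-28 (13 start days), with C2D1 on Day 29. A run of n days hides n - 2 starts.
- Now: 13 - 2 = 11, so 11/13 = 85% of start days are unseen.
- With Day 22: (6 - 2) + (6 - 2) = 8, so 8/13 = 62%.

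These are shares of start days, not risks.

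**Direction of the effect on 3+3.** With per-patient DLT probability p, a dose level passes with probability (1-p)^3 + 3p(1-p)^2 x (1-p)^3. If a share m of DLTs is missed, p becomes p(1-m). With assumed values:

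| True p | m = 0 | m = 10% | m = 25% |
|---|---|---|---|
| 0.20 | 0.709 | 0.752 | 0.814 |
| 0.33 | 0.434 | 0.500 | 0.605 |

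The documents give no value for m. The table shows the direction, not the size to expect.

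**The case against.** The strongest case on the other side is that this is a wording slip with little practical consequence.

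- **Week 4 is treatment-free, so weekly may mean treatment weeks.** The omission of Day 22 may well be deliberate; Appendix H shows the break as a separate row. But 7.3.2 speaks of the first cycle and 6.2.1 places the break inside it. Even if cycle 1 ended on Day 21, Days 16 to 21 would have no count.
- **Late marrow toxicity is unlikely.** This largely stands. The only time course given (5.5.3.3.3, thrombocytopenia with carfilzomib at 250 mg) has onset typically in the first week, which Day 8 covers. Section 1.1 reports 0% grade 3-4 neutropenia and thrombocytopenia with short-course radiotherapy alone, and 5.7.7 lists no hematological event. Against that, 1.3.2 lists decreased neutrophils in the three patients given TG02 200 mg with radiotherapy, without grade or timing. Grade 3 or 4 neutropenia in Group C also contributed to the lower doses (1.3.3.2).
- **A silent laboratory fall is not automatically a DLT.** This stands: clinical significance and relatedness must be judged. But an investigator cannot judge a count that was never taken. The exclusion of asymptomatic or reversible laboratory abnormalities belongs to the non-hematological criterion only.
- **Other safeguards exist.** Section 7.3.1 follows adverse events to resolution, so a low count found on Day 15 would be pursued. The 18.1 teleconference reviews each cohort, and unscheduled counts remain possible. None of these requires a count after the Day 18 dose.

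A reader might also infer that escalation will be decided on Day 15 data. That is only a worst case: 8.1.1 is permissive, and Cycle 2 Day 1 nominally falls the day after cycle 1 ends. Nor do the documents show that patients would be ruled unevaluable under 7.3.4. The review team has discretion, and nothing suggests it would fault the absence of a visit that Group A's schedule does not list.

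**Conclusion.** The inconsistency is real and should be corrected. On the nominal calendar Group A has a 14-day gap between scheduled counts (11 to 17 with the visit window), starting before the last combination TG02 dose and lying almost wholly inside the DLT window. A 7-day episode of neutrophils below 0.5 x 10^9/L starting on any of Days 16 to 22 would not be sampled.

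The conclusion assumes an event that is silent, resolves before Cycle 2 Day 1, prompts no unscheduled count, and would have been judged clinically significant and possibly related. Febrile neutropenia and bleeding would present clinically, and an event still present at Cycle 2 Day 1 would be found.

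It would be tempting to conclude that the Group A MTD cannot be relied on. The documents do not support that: they give no onset or duration data for TG02 with radiotherapy, and what they do give points to a low frequency. The supported conclusion is that the schedule leaves an avoidable hole in DLT capture whose only possible bias is towards the higher dose. A permitted radiotherapy delay (up to 7 days, 5.7.8) would lengthen the gap. No figure is put on that, because the plan does not say whether days after Day 28 still count for DLT.

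**What to change.** 1. Add a Day 22 hematology and biochemistry draw for Group A cycle 1 in 6.2.1.2, the 6.4.1 table and footnotes 7 and 8.
2. If Cycle 2 Day 1 falls after Day 29, through the visit window or a radiotherapy delay, continue weekly counts until that visit.
3. State in 8.1.1 or 18.1 that the end-of-cohort review uses, for each patient, a count taken after the Day 18 dose.
4. As a minor consistency correction, add Day 22 to Group B footnotes 7 and 8 (6.4.2). Group B's text (6.2.2.2) and table already list it. Group C is not a comparator, since 6.2.3.2 lets Days 15 and 22 be omitted and it has no DLT-based escalation.

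The cost is one routine draw per patient, up to 24 evaluable patients in Group A. It falls in a treatment-free week, so it may mean an extra trip, but 7.1.7 allows a local laboratory. A further draw is needed only when Cycle 2 Day 1 is late. Events of 6 days or less between weekly counts can still be missed.

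If the sponsor does intend Days 8 and 15 only, 7.3.2 should be corrected instead and the limit on DLT capture stated. That resolves the contradiction but leaves the gap.

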7.3.3 Toxic deaths

Toxic death is defined as death due to toxicity (defined as death from an AE for which there is a reasonable possibility that the study treatment caused the AE). The cause of death must be reported as "toxicity".

The evaluation of toxic deaths is independent of the evaluation of response (patients can die from toxicity after a complete assessment of the response to therapy).

7.3.4 Evaluability for safety

All patients who have started the treatment will be included in overall safety analyses.

For hematological events, the sponsor's medical review team may decide that blood counts have not been performed and/or reported according to the protocol and are therefore inadequate for the evaluation of one/several hematological parameters in some patients.

Patients who have discontinued treatment because of toxicity will always be included in the safety analyses.

7.4 Evaluation of frailty using the G8 geriatric screening tool

7.4.1 Background

Older cancer patients have a much more heterogeneous general health status compared to young cancer patients. Some older patients are in perfect general health, while others are vulnerable or frail. Frailty is a well-known concept in geriatric medicine (Ref. 45). It is defined as a multi-factorial syndrome, resulting in a reduction of the physiological reserve and of the capability to resist stressful events (homeostatic capacity). Frailty is associated with an increased risk of unfavorable clinical events: disability, hospitalization, institutionalization, death. In oncology, the construct of frailty is also used to describe patients with increased risk of treatment-associated morbidity and mortality. Presence of frailty can be detected by the (Comprehensive) Geriatric Assessment (GA). Performance of GA is advised in older cancer patients by the International Society of Geriatric Oncology, SIOG (Ref. 46). GA is time consuming (takes about 30 minutes). Therefore, short geriatric screening tools such as the G8 have been developed as a short and easy to use measurement of general health status. The G8 score has been specifically developed in oncology, includes 8 items, takes a few minutes to complete, and can be completed by any health care worker (Ref. 47). The score ranges from 1 to 17. A score greater than 14 indicates that there is little risk that further GA reveals significant problems in the further assessed GA domains. The G8 was shown to strongly predict functional decline and overall survival (Ref. 48). G8 is by far the best studied geriatric screening tool in oncological patients, and also has better performance for detection of geriatric problems than other geriatric screening tools such as VES-13 (Ref. 49).

7.4.2 Assessments

G8 will be measured in all patients in groups A and B. G8 has to be completed by the clinician, the nurse or the trained coder. This screening tool includes 7 items of the Mini Nutritional Assessment and the age of the patient. The English version of G8 is included in Appendix G.

7.4.3 Objective

The inclusion of the G8 screening tool in EORTC trials will allow a uniform, easy and established approach of frailty at baseline. The G8 tool itself has been developed as a screening tool, and not a tool for follow-up.

The treating physician may decide which actions are needed based on the G8 result (e.g. further geriatric assessment in case of a G8 score of less or equal to 14; geriatric interventions if specific problems are detected within specific geriatric domains).

The assessment of frailty as defined by G8 entered in EORTC trials will allow interpretation of whether new treatment strategies have been tested in both fit and less fit patients which has importance for the generalizability of the study results.

8 Statistical considerations

